## ANNEXURE - C

**Project Title:** Spatiotemporal gait parameters of healthy and stroke patients during overground, self-paced treadmill, and body-weight supported treadmill walking.

### **Summary:**

This study aims to collect and analyze spatiotemporal data from stroke patients using an in-house gait analysis setup. Each walking modality-overground, self-paced treadmill, and body-weight supported treadmill provides distinct advantages and challenges. Overground walking simulates natural conditions but lacks mechanical support; self-paced treadmill walking provides a controlled environment with adjustable speed; and body-weight supported treadmill walking reduces lower extremity pressure and the risk of falling. A locally made body weight support structure (BWSS) is used for fall prevention in hemiparetic patients during data collection. The BWSS includes: Hand winch system with locking mechanism, Double pulley system, An overhead harness, and A 10 ft Stainless steel wire (loading capacity=5 ton). For Overground, data collection is done using two force plates positioned in the middle of a linear pathway, an 8-camera video monitoring system, and AcqKnowledge software is used for data analysis. Data collection from the self-paced treadmill and body-weight supported treadmill also occur through the video monitoring system. Data collection will adhere to standard protocols to ensure safety and accuracy. Participants will walk along the pathway, and gait data will be recorded using the force plates and video system. By analyzing gait parameters such as step length, stride length, cadence, gait speed, and the duration of stance and swing phases, the study aims to identify which modality offers the most consistent and stable gait patterns, indicating improved motor control and coordination.

### **Introduction:**

Stroke is the leading cause of disability worldwide, affecting the lives of millions of people. One of the most debilitating effects of stroke is impaired gait, which impairs mobility and independence [1]. It is especially prevalent in low- and middle-income countries such as Bangladesh. Stroke is the third leading cause of death from non-communicable diseases in Bangladesh, putting a significant burden on both individuals and the healthcare system. Stroke prevalence in Bangladesh is around 11.39 per thousand people, with higher rates in rural areas and among elderly males [2]. Gait abnormalities are experienced by about 80% of stroke survivors, and they can significantly impair their daily activities and overall quality of life [3]. The significant number of disability-adjusted life years (485 per 10,000 people) lost due to stroke severely impacts the nation's economy [4]. Despite the high occurrence of disability due to stroke in Bangladesh, there are significant limitations in analyzing the gait characteristics of stroke patients. Gait rehabilitation uses a variety of walking modalities, such as body weight supported treadmill walking, self-paced treadmill walking, and overground walking. Every modality has particular benefits and drawbacks. The most natural kind of gait training is provided by walking on terrain that closely resembles actual walking conditions. However, because of the unpredictable nature of the environment and the lack of

mechanical support, it can be challenging for stroke patients [5]. Self-paced treadmill walking provides a controlled environment in which the patient's speed can be adjusted based on their abilities, allowing for a consistent walking rhythm and feedback [6]. This modality is useful for strengthening gait patterns and increasing endurance. However, body weight supported treadmill walking allows the patient to partially offload their weight, which lessens the pressure on their lower extremities and improves safety by lowering the chance of falls [7]. Variability in gait parameters such as step length, stride length, cadence, gait speed, and the duration of the stance and swing phases is an important aspect of gait analysis. High variability in gait frequently indicates instability and inefficiency, which are undesirable outcomes in rehabilitation. Lower variability, on the other hand, indicates more consistent and stable gait patterns, implying improved motor control and coordination.

### **Objectives:**

In this study, we aim to evaluate the gait differences among three different walking modalities with respect to spatiotemporal gait parameters. This will be achieved through a comparative analysis of spatiotemporal data between those groups. To ensure the safety of the subjects, the data collection protocols will be strictly followed, incorporating already tested procedures that have shown no probable risk. The BWSS has been tested with healthy individuals and is manufactured using widely available components in Bangladesh. The objectives of the study are as follows:

- **Study objectives:** To evaluate the variations in spatiotemporal gait parameters of three different walking modalities and analyze and determine which walking technique provides the most reliable gait metrics, suggesting a more stable and possibly advantageous recovery outcome.
- **Study Hypothesis:** We hypothesize that body weight supported treadmill walking will exhibit the least variability in spatiotemporal gait parameters compared to overground walking and self-paced treadmill walking. This suggests that BWST provides a more controlled environment, promoting more consistent and reliable gait patterns, which may translate to a more stable and potentially advantageous recovery outcome for individuals with stroke.

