**Date: 20/08/2024**

**Name of Co-investigator (S)**

**Signature**

**\* Include all the Investigator, Co-Investigators.**

**ANNEXURE - B**  
**ABSTRACT FOR**  
**BME Ethical Review Committee (BMEERC)**

The Ethical Review Committee will not consider any application which does not include a specific abstract/summary for the committee. The abstract should summarize the study's purpose, the methods, and procedures to be used by addressing each of the following items. If an item is not applicable, please note accordingly:

1. Describe the requirements in respect of the population and explain the rationale for using the population of special groups such as children, Incompetent person, or groups whose ability to give voluntary informed consent is questionable.

**Response:** The primary aim of the study is to evaluate the differences in variability in spatiotemporal gait parameters of stroke patients during overground, self-paced treadmill, and body-weight supported treadmill walking. Stroke, while more common in older adults, can affect people of all ages. As a result, our study participants range in age from 18 to 75 years, allowing us to better understand the impact of stroke across a larger age range. Children under the age of 18 and individuals who are unable to provide voluntary informed consent will be given consent from a parent or legally authorized guardian. Furthermore, consent will be obtained from children who are old enough to understand the study, ensuring that they are willing to participate. Pregnant women are not allowed to participate in the study due to safety concerns. The specific inclusion criteria are listed below:

*Post-stroke patients who are able to walk and aged between 18 to 75 (not pregnant).*

2. Describe and assess any potential risks - physical, psychological, social, legal or other and assess the likelihood and seriousness of such risks. If methods of research create potential risks, describe other methods, if any, that were considered and why they cannot be used.

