**Response:** The primary aim of the study is to compare the variability in spatiotemporal gait parameters of stroke patients across overground, self-paced treadmill, and body-weight supported treadmill walking, and to identify which walking technique yields the most consistent and beneficial gait metrics, indicating a more stable and effective recovery. If the post-stroke subject is afraid of falling, an overhead harness will be used to ensure their safety during data collection.

The use of the body weight support structure (BWSS), which is designed to help participants with balance issues, carries minimal physical risk. The structure can support up to 5 tons and has been tested on healthy adults weighing an average of 80 kg for up to 4 minutes. The overhead harness is intended to provide comfort by evenly distributing pressure across the lumbar and thoracic regions, and it includes a thigh belt for added safety. There may be some psychological discomfort due to unfamiliarity with the

equipment or the testing environment. There are no anticipated social or legal risks in this study.

3. Describe procedures for protecting against or minimizing potential risks and assessment of their likely effectiveness.

**Response:** The study is designed to minimize potential risks through careful planning and implementation of safety measures. The primary risk mitigation strategy involves using a body weight support structure during data collection for stroke subjects. This structure can support up to 5 tons and has been tested for safety and comfort. It includes an overhead harness to provide support during walking. During the data collection process, participants will be continuously monitored by the study investigators. Any signs of physical discomfort, fatigue, or deterioration in condition will result in the immediate termination of the experimental trial. Participants unable to walk with the overhead harness or express discomfort will not be subjected to the experiment.

4. Include a description of the methods for safeguarding confidentiality or protecting anonymity.

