### **Rationale:**

Stroke is a leading cause of disability worldwide, significantly impairing mobility and increasing the risk of falls. In Bangladesh, stroke is not only a major health concern due to its high prevalence and mortality rate but also has a substantial economic impact, with a large number of disability-adjusted life years lost. Despite the high incidence of stroke and the resultant gait impairments, there is a significant gap in the availability of gait analysis in Bangladesh. Most existing studies in

the region rely on traditional, observational methods that often provide inaccurate data and focus primarily on spatiotemporal parameters, neglecting crucial biomechanical insights.

Gait analysis, which measures characteristics such as stride length, step time, and swing time (spatiotemporal parameters), is critical for evaluating gait quality and monitoring rehabilitation progress. Overground walking analysis is widely regarded as the gold standard [8]. However, environmental factors such as uneven surfaces, obstacles, and a fear of falling can cause data variability [9]. Treadmill walking provides a controlled environment and facilitates data collection, but the question remains: which environment yields the most reliable and informative data for post-stroke gait assessment and rehabilitation planning?

This study fills this knowledge gap by investigating the variability of spatiotemporal gait parameters across three walking environments:

- Overground walking: Represents real-world walking but can be influenced by environmental factors, as previously stated.
- Self-paced treadmill walking provides a controlled environment, but may not fully challenge balance and coordination, potentially yielding less informative data on these aspects of gait.
- Body weight supported treadmill walking (BWST): Provides partial support, potentially promoting more consistent gait patterns due to lower balance demands, which may be beneficial for initial gait training.

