Understanding the variability of gait parameters across these environments is important for several reasons. Identifying the environment that produces the most consistent and reliable gait data enables researchers and clinicians to select the best assessment method for post-stroke patients. This can result in more accurate assessments of gait impairments and progress during rehabilitation. Therapists can tailor gait training programs to specific environments based on rehabilitation objectives and individual needs. For example, because of its supportive nature, BWST may be a useful tool for initial training, whereas overground walking practice becomes more critical as balance and coordination improve. Additionally, it will provide a reliable and safe method for gait analysis that can be widely adopted in Bangladeshi healthcare setting and lay the groundwork for future research and clinical applications in gait analysis and rehabilitation for stroke patients in Bangladesh. Ultimately, this study seeks to improve the assessment and management of gait impairments in stroke patients, contributing to better rehabilitation outcomes and enhancing the quality of life for affected individuals.

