### Phase-3-Extended Study (0):

The aim of this phase of study is to compare the Spatiotemporal parameter among different waking modalities. The standard protocols will be followed while conducting experiment, in the Department of Biomedical Engineering (BME), BUET. The various aspect of this final and most important component of the study are described below:

**Sample Size calculation:** In this comparative study, the gait velocity in between different waking modalities is considered as the primary parameters. The following formula may use for calculating the sample size for each group of the trial:

$$\text{Sample size, } N = \frac{2\sigma^2(Z_{1-\beta} + Z_{1-\alpha/2})^2}{d^2(k-1)} \quad \dots \dots \dots \quad (i)$$

Where,

N = Required sample size

$d$  = Difference in means of two group (effect size)

$$\sigma = \text{SD}$$

**k** = is the number of groups being compared.

$Z_{1-\beta}$  = It is the desired power

$Z_{1-\alpha/2}$  = Critical value and a standard value for the corresponding level of confidence. (At 95% CI it is 1.96)

To estimate the sample size, we considered the mean difference of the velocity of the post stroke patient to be at least 0.17 with a standard deviation of 0.3. We estimated that 24 individuals would be needed to satisfy the comparative studies between three groups, based on the statistical power of 80%, at a two-sided alpha level of 0.05. The statistical formula (i) used for the comparative test [10]. Considering dropouts and left-against-medical advice (LAMA) cases, sample size  $N = 25$  will be considered. Thus, a total of 25 subjects will be considered for the equal allocation of this study. The different aspects of the study are summarized in Table I.

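### The stated aim and only hypothesis concern gait variability, but the primary outcome and the sample size concern mean gait velocity

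*Protocol*

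**What the plan says.** **The question.** Annexure B, item 1: "The primary aim of the study is to evaluate the differences in variability in spatiotemporal gait parameters of stroke patients". Item 2: "The primary aim of the study is to compare the variability in spatiotemporal gait parameters of stroke patients". In Annexure C, the Summary says "the study aims to identify which modality offers the most consistent and stable gait patterns", and the Rationale describes the study as "investigating the variability of spatiotemporal gait parameters across three walking environments" and gives as a benefit "Identifying the environment that produces the most consistent and reliable gait data". The Introduction explains that high variability signals instability and low variability better motor control. The only hypothesis, under Objectives, is that "body weight supported treadmill walking will exhibit the least variability in spatiotemporal gait parameters", compared with overground and self-paced treadmill walking.

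**The primary outcome.** Sample Size calculation (Phase-3-Extended Study): "the gait velocity in between different waking modalities is considered as the primary parameters". On the inputs: "we considered the mean difference of the velocity of the post stroke patient to be at least 0.17 with a standard deviation of 0.3". In the formula, d is defined as a difference in means. Table 1 lists gait velocity as the primary outcome. Its six secondary lines are step length, stride length, cadence, stance and swing duration, single and double support time, and ground reaction force. The data analysis row of Table 1 names a comparison of the primary outcome, the Wilcoxon signed-rank and paired t tests, an intraclass correlation, and a mean difference with standard deviation.

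**The concern.** The primary outcome should measure what the primary aim asks. Here the aim is about how consistent each participant's gait is within a modality, while the primary outcome is how fast participants walk on average. These are different quantities. Participants may walk at different mean speeds in two modalities with the same step-to-step variability, or at the same mean speed with different variability.

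So the study could meet its primary outcome and leave its stated question unanswered. It could also draw a variability conclusion from a measure, a parameter and a contrast chosen after the data are seen. In both cases the quoted 80% power belongs to a question other than the hypothesis.

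**Working it through.** **1. The protocol's own figure.** Inputs from Sample Size calculation: d = 0.17 (difference in mean velocity, no unit given), σ = 0.3, k = 3, power 80%, two-sided alpha 0.05.

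N = 2σ²(z₀.₈₀ + z₀.₉₇₅)² / [d²(k − 1)] = 2 × 0.3² × (0.8416 + 1.9600)² / (0.17² × 2) = 24.44.

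The protocol states 24 and adds one for dropouts, giving 25. The figure reproduces to rounding. Every effect input concerns mean velocity; none is a within-participant SD, a coefficient of variation (CV) or a ratio of variabilities.

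**2. Outcomes set against the aim.**

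| Place | What is stated | Variability measure? |
|---|---|---|
| Annexure B, items 1 and 2 | Primary aim: compare variability | Asked for |
| Objectives, hypothesis | Body-weight-supported treadmill least variable | Asked for |
| Sample Size calculation | Difference in mean velocity | No |
| Table 1, outcomes (1 primary + 6 secondary = 7 lines) | Gait parameters | 0 of 7 |
| Case Report Form, items 24–35 (12 items) | Gait parameters | 0 of 12 |

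**3. What N = 25 offers for a variability score.** Suppose each participant has one variability score per modality and two modalities are compared by paired t test. At 80% power and two-sided 0.05, the noncentral t distribution gives the detectable standardised difference (mean difference divided by SD of the paired differences):

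- 25 completers: 0.584
- 24 completers: 0.597

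For comparison, the velocity assumption is 0.17 / 0.3 = 0.567. If 0.3 is read as the SD of paired differences (an assumption), the standardised sensitivity is similar. What is missing is any statement of how large the variability difference is expected to be. No required N for the hypothesis can be computed from the document.

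**4. How well overground variability can be measured.** Data collection procedure plans two overground walks and gives no stride count. Assume m independent, normally distributed strides per walk, with the two within-walk variances averaged. Then df = 2(m − 1), and the standard error of one participant's log SD is 0.5 × √trigamma(df/2):

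| m (assumed) | df | SE of log SD |
|---|---|---|
| 3 | 4 | 0.402 |
| 6 | 10 | 0.235 |
| 10 | 18 | 0.171 |
| 20 | 38 | 0.116 |

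With few strides per walk, the overground score would be imprecise for each participant.

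**The case against.** The best defence is that the document carries two aims. The opening of Objectives and the phase aim before the sample size speak broadly of comparing gait parameters between modalities, which fits mean velocity. The word variations in the objective can also be read as differences. Table 1 does name a standard deviation and an intraclass correlation, and one objective concerns reliable metrics. The exact variability formula could sit in a statistical analysis plan, and the video recordings could support either question later.

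Part of this stands. The broader wording is there. The listed tests are not at fault, since a paired t or Wilcoxon test works on a per-participant variability score. The case report form is weak evidence: it has no separate fields by modality even for velocity, so it may not mirror the analysis dataset.

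The rest does not remove the conflict. Broad wording does not override two explicit statements of the primary aim and the only hypothesis. An intraclass correlation between modalities does not rank them by variability. A standard deviation across participants mixes differences between people with stride-to-stride consistency. Neither is tied to the hypothesis or made an outcome. An analysis plan can supply a formula, but it cannot make the protocol's stated primary outcome measure its stated primary aim.

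**Conclusion.** The concern holds and should be fixed before data collection. The primary outcome does not measure the primary aim, and nothing in the protocol reconciles the two. None of the 7 outcome lines is a variability measure, and N = 25 with 80% power was derived for mean velocity alone.

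This does not show that 25 participants are too few. The figure of 0.58 (0.60 with 24 completers) assumes one paired comparison at two-sided 0.05 and is a benchmark only. The precision figures rest on assumed stride counts. The finding itself rests only on the protocol's wording.

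**What to change.** Reconcile the sections in one of two ways.

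**(a) Preferred, because the stated primary aim and the hypothesis ask about variability.**

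- In Table 1, make one named per-participant variability measure the primary outcome, for example the within-walk stride-to-stride CV or log SD of one parameter chosen by the investigators. Move mean gait velocity to secondary.
- Compute it from a comparable number of strides in each modality, averaging within-walk variances over the two overground walks.
- Compare body-weight-supported treadmill with overground, and with self-paced treadmill, using the paired tests already listed. Claim least variability only if both comparisons are significant.
- Add fields by modality for the measure and its stride count to the Case Report Form.
- State in Sample Size calculation that N = 25 and 80% power were derived for mean velocity, and give the detectable difference for the variability measure (about 0.58 SD of the paired difference with 25 completers).

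Cost: text and form edits. Video is already planned in all three modalities and no extra participants are required by this change, but longer or more overground walks might be needed for enough strides. Requiring both comparisons lowers power by an amount that depends on effects the protocol does not give.

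**(b) Keep mean velocity as primary.** Restate the aim and hypothesis as a comparison of mean velocity in Annexure B items 1 and 2 and in the Summary, Objectives and Rationale of Annexure C, and align the Introduction and the Table 1 objective. Drop the conclusion about the least variable or most consistent modality. Cost: text edits and the loss of that conclusion.

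Under the undertaking in Annexure A, either route needs ethics committee approval before it is made.

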### **Rationale:**

Stroke is a leading cause of disability worldwide, significantly impairing mobility and increasing the risk of falls. In Bangladesh, stroke is not only a major health concern due to its high prevalence and mortality rate but also has a substantial economic impact, with a large number of disability-adjusted life years lost. Despite the high incidence of stroke and the resultant gait impairments, there is a significant gap in the availability of gait analysis in Bangladesh. Most existing studies in

the region rely on traditional, observational methods that often provide inaccurate data and focus primarily on spatiotemporal parameters, neglecting crucial biomechanical insights.

Gait analysis, which measures characteristics such as stride length, step time, and swing time (spatiotemporal parameters), is critical for evaluating gait quality and monitoring rehabilitation progress. Overground walking analysis is widely regarded as the gold standard [8]. However, environmental factors such as uneven surfaces, obstacles, and a fear of falling can cause data variability [9]. Treadmill walking provides a controlled environment and facilitates data collection, but the question remains: which environment yields the most reliable and informative data for post-stroke gait assessment and rehabilitation planning?

This study fills this knowledge gap by investigating the variability of spatiotemporal gait parameters across three walking environments:

- Overground walking: Represents real-world walking but can be influenced by environmental factors, as previously stated.
- Self-paced treadmill walking provides a controlled environment, but may not fully challenge balance and coordination, potentially yielding less informative data on these aspects of gait.
- Body weight supported treadmill walking (BWST): Provides partial support, potentially promoting more consistent gait patterns due to lower balance demands, which may be beneficial for initial gait training.

Understanding the variability of gait parameters across these environments is important for several reasons. Identifying the environment that produces the most consistent and reliable gait data enables researchers and clinicians to select the best assessment method for post-stroke patients. This can result in more accurate assessments of gait impairments and progress during rehabilitation. Therapists can tailor gait training programs to specific environments based on rehabilitation objectives and individual needs. For example, because of its supportive nature, BWST may be a useful tool for initial training, whereas overground walking practice becomes more critical as balance and coordination improve. Additionally, it will provide a reliable and safe method for gait analysis that can be widely adopted in Bangladeshi healthcare setting and lay the groundwork for future research and clinical applications in gait analysis and rehabilitation for stroke patients in Bangladesh. Ultimately, this study seeks to improve the assessment and management of gait impairments in stroke patients, contributing to better rehabilitation outcomes and enhancing the quality of life for affected individuals.

